1. INTRODUCTION

The study design presented in this non-interventional study protocol will provide an evaluation of the characteristics of patients under specialist (psychiatrist) care receiving Seroquel XR as treatment for MDD. The study will also summarize data on prescribing and drug utilisation of therapeutic regimens used to treat MDD that include Seroquel XR, and document any differences in prescribing patterns between the countries included in the study. This study will be conducted in 5 European Union countries representing different geographic regions.

1.1 Study objectives

The study objectives include:

- documenting characteristics of patients under specialist (psychiatric) care who are prescribed Seroquel XR as treatment for MDD in each of the selected countries over a 9 month period, starting 3 months following the launch of the product for its approved indication.
- describing the differences between countries concerning treatment practices involving use of Seroquel XR through the use of a drug utilisation questionnaire of psychiatrist in 5 European countries.

2. STUDY DESIGN

This non-interventional study protocol has been subject to a peer review according to AstraZeneca standard procedures.

2.1 Overall study design

This is a multinational, multicenter, retrospective, observational study of antidepressant drug utilisation among an inception cohort of patients under specialists (psychiatrists) care who are prescribed Seroquel XR for treatment of major depressive episodes associated with MDD following launch of the indication in each country. The study will be conducted in 5 European countries: Germany, Italy, Romania, Spain, and Sweden to ensure geographic representation across European member states. The sponsor may include alternate EU country(ies) based upon limited use of Seroquel XR for MDD in the countries listed and whose selection will maintain geographic representation among EU countries.

The inception cohort is defined as patients initiating Seroquel XR (as add-on therapy or as monotherapy) during a 9 month period corresponding to 3 to 12 months following the launch of the product in each country for the MDD indication. In the period immediately after launch, physicians may not be aware of the approval of Seroquel XR for add-on treatment for MDD. Therefore, patients treated with Seroquel XR within the 3 months after launch will not be included in the inception cohort because they are not likely to be representative of patients

[figure not shown]
treated in subsequent periods. A drug utilisation questionnaire will be used to collect study data. Data collection will be initiated following a study-defined index date, approximately 12 months after product launch. All study sites within a country will be assigned the same index date and will not be contacted prior to the index date.* Initiation of site-specific activities for selection of patient records meeting study selection criteria will commence on or following the index date. Data on drug utilisation will be censored on the index date. This approach will ensure that study procedures do not influence prescribing practices.

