4.2 Questionnaire Administration

4.2.1 Timeline for questionnaire administration

The exact index date for each country will be selected to optimise preparations leading to completion of drug utilisation questionnaires at all sites within a country following Good Pharmacoepidemiology Practices (PDS 2008).

Contact with investigators and site preparatory activities are initiated following the index date, which will correspond to a date approximately 12 months following the launch of Seroquel XR for MDD in each country.

Preparatory activities for completion of the drug utilisation questionnaires at each site will rely on automated and manual review of data from patient medical records in order to identify patients meeting study inclusion criteria. This selection includes consideration of the inception cohort definition (i.e., initiation of treatment with Seroquel XR in the time interval 3 months after launch up to the index date).

Once site preparatory activities are concluded, including the obtaining of informed consent from the patient, data abstraction of patient medical records using the drug utilisation questionnaire will begin.

Information on the Physician questionnaire related to physician characteristics will be completed based upon the best available recollection by the investigator. Patient questionnaire data will be abstracted from the medical records of the patients maintained at the official location for storage of records for the site/investigator and will be performed by a representative of AstraZeneca.

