9.4 Other drug utilisation for MDD

The following will be summarized for treatments other than Seroquel XR for MDD the daily dose at the first initiation, whether a dose change accompanied initiation of Seroquel XR, latest dose following Seroquel XR initiation, interval from initiation of Seroquel XR to latest dose change and whether the prescription was continuing on the index date.

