(1) Specific drug name (generic or brand names)	(2) Start date (day/mth/year) Check for “on demand” or prn use)	(3) End Date (day/mth/year)	(4) Dose (specify Unit)	(5) Did the dose change at initiation of Seroquel XR?	(6) Most recent dose prior to [INDEX DATE] (if different than at initiation)	(7) Date of most recent dose change (day/mth/year)
	___/___/___  prn	___/___/___  Still prescribed at [INDEX DATE]	_____	 Increase  Decrease  Remained the same  Not applicable	_____  Not applicable	___/___/___  Not applicable
	___/___/___  prn	___/___/___  Still prescribed at [INDEX DATE]	_____	 Increase  Decrease  Remained the same  Not applicable	_____  Not applicable	___/___/___  Not applicable
	___/___/___  prn	___/___/___  Still prescribed at [INDEX DATE]	_____	 Increase  Decrease  Remained the same  Not applicable	_____  Not applicable	___/___/___  Not applicable
	___/___/___  prn	___/___/___  Still prescribed at [INDEX DATE]	_____	 Increase  Decrease  Remained the same  Not applicable	_____  Not applicable	___/___/___  Not applicable

Seroquel XR Treatment

Was the patient experiencing psychotic symptoms at initiation of Seroquel XR?

- Yes
- No
- Unknown

Which disorder was Seroquel XR prescribed for?

Please select all that apply

- MDD
- Schizophrenia
- Bipolar disorder
- Other – please specify _____

How many times has the investigator seen this patient since initiation of Seroquel XR?

__ visits

What is your estimate of patient adherence to the prescribed treatment regimen that included Seroquel XR for depression?

___ % of time adherent to prescribed dose(s) (range: 0 – 100%)

(Investigator assessment)

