In the table below record the number of different **dosages of Seroquel XR** prescribed for this patient. Please indicate by ticking in the appropriate boxes the **different dosages** that this patient has experienced, then please enter the **number of prescriptions** for each selected dosage and the **duration (or days supply) of each prescription**.

Dosage of Seroquel XR prescribed	Number of prescription for each dosage	Duration of each prescription (in days)
 50 mg / day	__ scripts	Script 1: __ days, Script 2: __ days, Script 3: __ days, Script 4: __ days Script 5: __ days, Script 6: __ days, Script 7: __ days, Script 8: __ days
 100 mg / day	__ scripts	Script 1: __ days, Script 2: __ days, Script 3: __ days, Script 4: __ days Script 5: __ days, Script 6: __ days, Script 7: __ days, Script 8: __ days
 150 mg / day	__ scripts	Script 1: __ days, Script 2: __ days, Script 3: __ days, Script 4: __ days Script 5: __ days, Script 6: __ days, Script 7: __ days, Script 8: __ days
 200 mg / day	__ scripts	Script 1: __ days, Script 2: __ days, Script 3: __ days, Script 4: __ days Script 5: __ days, Script 6: __ days, Script 7: __ days, Script 8: __ days
 250 mg / day	__ scripts	Script 1: __ days, Script 2: __ days, Script 3: __ days, Script 4: __ days Script 5: __ days, Script 6: __ days, Script 7: __ days, Script 8: __ days
 300 mg / day	__ scripts	Script 1: __ days, Script 2: __ days, Script 3: __ days, Script 4: __ days Script 5: __ days, Script 6: __ days, Script 7: __ days, Script 8: __ days
Other 1: _____ mg / day	__ scripts	Script 1: __ days, Script 2: __ days, Script 3: __ days, Script 4: __ days Script 5: __ days, Script 6: __ days, Script 7: __ days, Script 8: __ days
Other 2: _____ mg / day	__ scripts	Script 1: __ days, Script 2: __ days, Script 3: __ days, Script 4: __ days Script 5: __ days, Script 6: __ days, Script 7: __ days, Script 8: __ days
Other 3: _____ mg / day	__ scripts	Script 1: __ days, Script 2: __ days, Script 3: __ days, Script 4: __ days Script 5: __ days, Script 6: __ days, Script 7: __ days, Script 8: __ days

Prior to initiating SEROQUEL XR, what was the patient response to their most recent prior antidepressant treatment?

		Side effects			

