		None	Did not significantly interfere with Subject's functioning	Significantly interfered with Subject's functioning	Outweighed therapeutic effect (Not tolerable, Needed to stop medication)
Therapeutic effect	Marked vast improvement. Complete or nearly complete remission of all symptoms				
	Moderate improvement. Partial remission of symptoms				
	Minimal slight improvement				
	Unchanged or worse				

Unknown or Not assessed
(Investigator assessment)

When was the last consultation date for this patient?

__ / __ / ____
day / mo / year

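### The end-date column of the concurrent-treatment table has no way to record an unknown status, so the summary of drugs continuing on the index date may mix documented with assumed continuation

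*Protocol*

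**What the plan says.** - **Cut-off.** Protocol Section 2.1: "All study sites within a country will be assigned the same index date", about 12 months after launch, and "Data on drug utilisation will be censored on the index date". Patients start Seroquel XR "during a 9 month period corresponding to 3 to 12 months following the launch", so possible follow-up to the cut-off runs from 0 to about 9 months.
- **Source.** Section 4.2.1 takes patient data from medical records "maintained at the official location for storage of records for the site/investigator". Sections 4.2.2, 7.3 and 8.1 also allow related records. Section 4.2.2 asks for drug data only where they are recorded.
- **Form.** In the Appendix B table of concurrent MDD drugs, column 3 takes an end date or the box "Still prescribed at [INDEX DATE". It has no unknown option. Columns 5 to 7 of the same table have a not-applicable box, and many other items on the form offer an unknown box.
- **Analysis.** Section 4.2.2 lists continuation on the index date as a variable to collect. Section 9.4 plans to summarise "whether the prescription was continuing on the index date" for MDD treatments other than Seroquel XR. Section 9 reports drug use by country and rules out imputation.
- **Related items.** For Seroquel XR only, the form records the number of scripts per dose and "Duration of each prescription (in days" of each. The last item asks "When was the last consultation date for this patient", with no limit relative to the index date.

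**The concern.** A chart documents continuation only for as long as something is entered in it. Take a patient who was discharged, was transferred or did not return, whose last entry shows an open antidepressant prescription some time before the index date. The true answer in column 3 is that the status is not known, and the form cannot record that. Three entries are possible: the continuation box, an end date that is not in the chart, or a blank. The protocol gives no rule for choosing, so abstractors may differ.

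Once the box is ticked, a drug assumed to be continuing looks the same as one documented as continuing. A blank stays missing. A later analysis plan cannot recover a distinction that the form did not capture.

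The affected result is the continuation summary in Section 9.4. It covers the other MDD drugs, for which the form collects no days' supply, so there is no second source to fall back on. Describing differences in treatment practice between countries is a stated objective (Section 1.1), so uneven handling between countries would matter.

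**Working it through.** The protocol states no figure for continuation or for early-ending records, so there is no stated result to reproduce. The check has three parts.

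**1. What each entry does to the Section 9.4 summary (records end early, no stop noted)**

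| Entry in column 3 | Effect |
|---|---|
| Continuation box | Counted as continuing; right or wrong, but not documented |
| End date not in the chart | Counted as stopped on an assumed date |
| Blank | Missing; not imputed (Section 9) |

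**2. Bound on the error.** Let t be the proportion ticked as continuing and f the proportion of all patients who are ticked without a record covering the index date. If the remaining ticks are right, true continuation lies between t − f and t, so the overstatement is at most f. With the f group set aside as not known, the proportion among those with known status is (t − f)/(1 − f).

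Assumed inputs, not in the documents: f = 5%, 10%, 20%, and t = 76%, chosen only because it is a row of Table 2.

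| f | True continuation lies in | Among known status |
|---|---|---|
| 5% | 71% to 76% | 0.71/0.95 = 74.7% |
| 10% | 66% to 76% | 0.66/0.90 = 73.3% |
| 20% | 56% to 76% | 0.56/0.80 = 70.0% |

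As a yardstick, the Table 2 half-width is 1.96 × √(p(1 − p)/n). At p = 0.76 this gives 8.4 points (n = 100), 5.9 (n = 200) and 4.2 (n = 400), matching the printed intervals. All 64 intervals in Table 2 reproduce to within 0.05 points. The maximum error at f = 5% exceeds the half-width at n = 400 but not at n = 200 or n = 100. At f = 10% or 20% it exceeds all three.

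**3. Seroquel XR duration.** If durations were run to the index date from column 3, the mean would be overstated by at most f × gap. With assumed gaps of 30 to 90 days, that is 0.05 × 30 = 1.5 days to 0.20 × 90 = 18 days. Section 9.3, however, reports duration as prescribed, and the script table gives days per script by dose. Duration can be built from those entries without running to the index date.

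**The case against.** The case on the other side has several parts.

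- **The cut-off sentence is not the fault.** A reader might infer from Section 2.1 that every patient is treated as observed to the index date. The sentence sets an outer limit, and the section gives its purpose: to keep study procedures from influencing prescribing. It does not claim complete observation. This stands.
- **The study measures prescribing, not intake.** A patient who stops taking a drug that is still prescribed is not misclassified. Only an unrecorded end of prescribing counts. This stands and narrows the problem.
- **Much of the drug data is unaffected.** Initial dose, maximum dose, drugs that ended before Seroquel XR and script days do not depend on column 3. A reader might infer that Seroquel XR durations are wrong, but the documents do not support that, for the reason in part 3 of the working.
- **A country bias is not shown.** The university and community hospital columns of Table 1 add to 30% in Romania and 60% in Germany (N/A counted as zero). A reader might infer more early-ending charts where the hospital share is higher. Table 1 describes psychiatrists' practice settings, Section 3.1 warns that the distribution of patients could differ, and nothing says that hospital charts end early. The inference is speculative.
- **Other safeguards exist.** These are related records, trained abstractors, standard scripts, queries and a form that may be revised after piloting. Consent is sought after the index date, which probably reduces the number of patients lost to the practice. These may make the problem less frequent, but none of them gives column 3 a way to record an unknown status.
- **The analysis plan may settle derivations.** It can say how the last consultation date is used. It cannot separate documented from assumed ticks after the event.

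**Conclusion.** The point holds in a limited form. Column 3 of the concurrent-treatment table cannot record that status on the index date is unknown, so the Section 9.4 summary of other MDD drugs still prescribed on that date may combine documented and assumed continuation.

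The size cannot be derived from the protocol. The upper bound equals the share of patients affected and ticked: 5 to 20 points if that share is assumed to be 5% to 20%. The bound is reached only if every such patient is ticked and in every case prescribing had in fact ended. Some will truly have continued, and some entries will be blank.

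It would go too far to say that such patients necessarily get a wrong status, or that all drug-use data are affected. The reason to act is that the remedy is nearly free and the information cannot be recovered once the form has been completed.

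**What to change.** 1. **Appendix B, concurrent-treatment table, column 3:** add a box reading 'Not known: no record covering [INDEX DATE]'.
2. **Abstractor instructions:** tick the continuation box only when the record supports it, and do not enter an end date that is not in the record.
3. **Section 9.4:** report continuing, stopped and not known as three categories by country.
4. **Last consultation date:** leave the present item unrestricted, because a consultation after the index date can show that the patient was followed through it. Add a second item for the last consultation on or before the index date. Together they help identify patients not followed to that date, although contact for consent, if charted as a consultation, could hide an earlier gap.

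Do not replace the index-date cut-off with censoring at the last visit. The other MDD drugs have no days' supply on the form, and most patients will not have been seen on the index date itself. True continuers would be cut off, and differences in visit frequency could look like differences in prescribing.

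The cost is one tick box, one date item, one instruction and one extra table category. The not-known group becomes visible and the continuation figure may be lower.

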2.1.1 Sampling Design

Sampling to identify patients will follow a two-step process. Study sites and investigators will be selected in the first step and individual patients in the second.

A sample of psychiatry practices within a country will be selected to reflect the overall distribution of practice settings in that country. This approach permits the inclusion of patients prescribed Seroquel XR by physicians practicing across different care settings where the medical management of MDD might differ.

Figure 1 – Overall Study Design

Note - In the period immediately after launch, physicians may not be aware of the approval of Seroquel XR for add-on treatment for MDD. Therefore patients treated with Seroquel XR within the 3 months after launch will not be included in the inception cohort because they are not likely to be representative of patients treated in subsequent cohorts.

* Local ethics approval for this protocol will be obtained prior to study start and prior to the study-defined index date.

3. SITE AND PATIENT SELECTION CRITERIA

3.1 Site and Investigator Selection

MDD patients may seek psychiatric care in a variety of settings, including mental health centers (MHC), university-affiliated hospitals, community hospitals, and in private practice settings. The distribution of psychiatry practice settings by country is expected to approximate the data provided in Table 1. Additional information on the settings of specialist care for MDD patients in each country will be obtained through consultation with Science Advisory Board Members. Any advice and updated information on the distribution of practice settings will be considered in investigational site recruitment in each country.

Approximately 25 sites/investigators will be selected in each country to permit the selection of MDD patients that are broadly representative of the overall MDD population.

Table 1 Distribution of Psychiatry Practice Settings by Country

Country	Number of Psychiatrists	MHC	Private Practice	University Hospital	Community Hospital
Germany	6040	N/A	40%	30%	30%
Spain	5782	41%	7%	36%	16%
Sweden	2196	45%	10%	45%	N/A
Italy	9117	40%	10%	20%	20%
Romania	1013	60%	10%	30%	N/A

Source for estimated number of psychiatrists (except Sweden and Romania): IMS. Sources for Sweden and Romania: WHO Report Policies and practices for mental health in Europe: meeting the challenges, 2008, xiii and The World Bank population statistics. The distribution of psychiatry practice settings was derived through disease-specific surveys, panels of independent scientific advisors for other neuroscience studies conducted by AstraZeneca, and based upon the literature. Based upon feedback from Science Advisory Board Members the proportion of patients treated for MDD could differ from the distribution of psychiatry practice settings provided in Table 1.

Investigators who have participated in the Seroquel XR clinical development program for MDD will be excluded from participation in this study.

3.2 Patient Selection

Each investigator will identify patients who meet criteria as having received SEROQUEL XR for MDD at any time in the 3-12 month period following launch in each country, and contact the patients to obtain informed consent. A listing of subjects will be generated according to patients' last name (or other convenient identifier).

Up to 30 subjects will be selected per site. The selection of eligible patients will proceed as follows:

1. For sites with 30 or fewer eligible patients, all will be included, provided that informed consent is given where required.
2. For sites with more than 30 eligible patients, random selection to assure lack of bias in the selection of 30 patients will be accomplished using an algorithm provided by AstraZeneca. Informed consent will be obtained to provide up to a maximum of 30 selected patients.

The limit of 30 patients per site is proposed to support the objective of having adequate representation of patients within a given country.

Site specific activities related to the selection of patient records will start on or following the index date. This approach should ensure that selection of patients will not be influenced by prescribing practices prior to the index date and prescribing practices are not influenced by study procedures.

If the number of eligible patients refusing to take part in the study exceeds 20% of the total sample in a country, readily identifiable basic demographic information (age range and gender) from patients refusing to participate will be requested and collated. This will permit an evaluation of the distribution of non-participants across sites and countries.

3.3 Inclusion and Exclusion Criteria for Patients and Investigators

Each patient and investigator should meet all inclusion criteria and none of the exclusion criteria for this study. Under no circumstances can there be any exceptions to this rule.

3.3.1 Inclusion Criteria for Patients

1. Provision of informed consent before initiation of any collection of questionnaire data.
2. Female and male aged 18 years and over.
3. Documented clinical diagnosis of Major Depressive Disorder, Single Episode, or Recurrent.
4. Initiation of Seroquel XR for treatment of MDD during the period defining the inception cohort, i.e. from 3 months after launch until the index date.

The prescription of the medicinal product is clearly separated from the decision to include the patients in the study.

3.3.2 Exclusion criteria for Patients

If participating in any clinical trial during the time from 3 months after launch until the index date, the patient cannot take part in this study.

